[name] Protocol and

Statistical Analysis Plan

PI: [name] MD MSc

NCT04969289

Department of Emergency Medicine

Version 4.11.22

Study Purpose and Rationale

Adolescents frequent the emergency department (ED), making up more than 19 million visits each year. Adolescent ED patients admit to infrequent condom use, with rates as low as 40% at last intercourse. Adolescent sexually transmitted infection (STI) detection rates in the ED are as high as 26%, depending on symptomatology. For many of these adolescents, the ED is their only source of medical care, and their communication with outpatient medical providers around sexual health topics is poor, especially regarding effective contraceptives. The ED visit is a potential missed opportunity to educate and motivate these males to participate in healthy sexual practices.

ED-based digital interventions are a way to educate, motivate, and facilitate behavior change. In the ED, wait times can be long, resources are limited, and medical providers are busy. Digital interventions targeting ED patients, such as those that screen and briefly intervene have reduced risky behaviors, such as alcohol misuse, violence, and aggression. Technological interventions in the ED show promise to improve depression symptoms, increase STI testing, and increase contraceptive initiation. Yet, it remains unknown if an adolescent male sexual health intervention is potentially efficacious in the ED setting.

The objective of this study to conduct a pilot randomized controlled trial (RCT) of an ED-based sexual health intervention, entitled [name] (Emergency Room Interventions to Improve Care). We hypothesized that [name] will be feasible in the ED setting, be acceptable to male ED patients, demonstrate fidelity, be adopted by users, and show potential efficacy to increase condom use.

Study Design, Procedures, and Data Analysis

Strategy and Sample:

We will conduct a pilot randomized controlled trial of up to 130 sexually active adolescent males aged 14-21 years who have been sexually active with females in the past 3 months. Exclusion: (1) do not own a mobile phone, (2) are too ill per the attending, (3) are cognitively impaired, (4) do not speak English, (5) want their partner to become pregnant in the next year, (6) are known COVID positive, (6) want their sexual partner to become pregnant in the next year, or (7) were previously enrolled in any of our qualitative interviews evaluating the [name] app. We will purposively sample males ages 14- 17 and 18-21. All patients, regardless of chief complaint, are eligible for screening.

Study Procedures

Recruitment and Safety:

We will recruit participants at our single center from the Pediatric Emergency Department and Adult Emergency Department. A member of the research team will identify potentially eligible patients using the electronic medical record (EMR). Our EMR reveals the age of each patient. The research team member will ask the medical provider caring the patient if we can approach the patient.

The study team will approach the potential participant as per standard practice of first checking that the treating physician has deemed the patient clinically stable and potentially appropriate for the research study. The research coordinator will introduce the study in accordance with the emergency medicine exemption policy and present the letter from the study PI and Medical Directors of the Emergency Departments. A member of the research team will then privately confirm eligibility and explain the study in full to the eligible patient in a private location by reviewing the informational form and answering all questions. If the patient is willing to discuss the study with a member of the study team, the research coordinator will proceed with consenting the subject. If the patient or/and family would like to talk to their treating physician more about the study, that will occur.

Research coordinators will screen ED patients during consecutive hours, Monday-Friday, 8am to 10pm, with some limited time for enrollment during weekend hours. Participants will be enrolled with informed consent. For participants aged 14-17, we will obtain 2-person verification of agreement to participate such as the research coordinator and ED attending. Participants will receive a \$10 gift card for enrollment.

Participants will be assigned to intervention versus usual care arm with 1:1 allocation ratio by using a computer-generated block randomization. We will conceal allocation by using sequentially numbered envelopes which were opened after consent. Neither the research team member nor the patient will be blinded to arm assignment; outcome assessors will be blinded. Participants will receive a \$10 gift card.

Standard care (SC) arm:

Participants randomized to the SC arm will receive standard medical care as determined by the ED provider, which is typically referral to a primary care or adolescent provider. Mobile telephone numbers will be collected for follow up purposes.

[name] arm:

After consenting, participants will interact with an ED-based iPad and the [name] app for a recorded period of time. The goal of [name] is to educate and motivate adolescent males to both use condoms and communicate with their sexual partners about effective contraceptive methods. The [name] app consisted of two parts—an ED-based app consisting of tailored educational sexual health modules followed by 10 weeks of once-a-week interactive text messages.

All participants will complete a brief survey to assess his acceptability of the app. The participant enters his phone number and then receives a welcome text. After ED discharge, we will send texts directly to the participant's phone via short message service (SMS). Texts are sent every 7 days for a total of 12 text message cascades.

As an incentive and thank you for completing follow up, those in both the [name] arm and SC arm will have the option to receive a one-time shipment of condoms in discrete packaging sent to their home address. This is voluntary and opt-in. The participants will indicate their decision within the [name] app and/or verbally, privately to the research coordinator.

Participants will complete a baseline questionnaire to assess demographics, access to care, as well as sexual behaviors, beliefs, and attitudes. Follow up data will be collected from both arms any of the following ways: (1) online survey texted at 6 weeks and 3 months after enrollment; (2) if no response in one week, then we email the link to the survey; and (3) phone follow up and/or text weekly until completion.

Data Storage:

Consent: Participants will review the consent on the iPad. No signature will be required.

Baseline questionnaire and follow up questionnaires: We will use a password-protected system.

Enrollment and follow up logs: We will store all data in the Microsoft Teams.

Outcomes:

We will evaluate established health service implementation measurements. *Feasibility* is the extent to which the innovation can be used in this setting. *Acceptability* is the extent to which the innovation was agreeable to a stakeholder. *Adoption* is the user's intention or decision to use the intervention. *Fidelity* is the extent to which an intervention is used as intended.

Our primary efficacy outcome is condom use. This self-reported outcome will be calculated within each group by dividing the total number of episodes of vaginal intercourse by the total number of times a male condom was used during vaginal intercourse over the past 4 weeks via self-report. This outcome has been used in prior RCTs and is associated with decreased pregnancy risk and STIs. Additional secondary outcomes were also collected.

Statistical Analysis Plan

All data will be analyzed using IBM SPSS®. We will summarize implementation outcomes using standard descriptive statistics. To determine our primary efficacy outcome, condom use at 6 and 13 weeks, we will analyze a per protocol population which included all randomized patients who complete follow up and were sexually active in the past 4 weeks. We will report percentages of condom use (number of sexual encounters using a condom / number of sexual encounters over the past 4 weeks via self-report) within each arm. We will also build a multiple logistic regression model of proportion of condom use (number of sexual encounters using a condom / number of sexual encounters over the past 4 weeks via self-report) adjusting for age (as a continuous variable) and baseline consistent condom use (as a binary variable) with arm as the main predictor. We also will use this model to measure additional binary secondary outcomes at 6 and 13 weeks including consistent condom use and condom use at last intercourse. We will perform a sensitivity analysis of our primary outcomes by removing outliers who may have skewed the model. We will also perform descriptive statistics on additional secondary outcomes and assess differences between those who were lost to follow-up and those who were not.

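### Optional, low-priority improvement: the primary model carries baseline condom use only as a yes/no flag; adding the baseline 4-week proportion, if it is collected, may gain power

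*Combined protocol and SAP*

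**What the plan says.** The Statistical Analysis Plan specifies a "multiple logistic regression model of proportion of condom use", where the proportion is "number of sexual encounters using a condom / number of sexual encounters over the past 4 weeks via self-report". The model is fitted "adjusting for age (as a continuous variable) and baseline consistent condom use (as a binary variable) with arm as the main predictor". No other baseline measure of condom use enters it. The same model is then applied to two binary secondary outcomes, consistent use and use at last intercourse.

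Four other statements bear on the point:
- The trial is a "pilot randomized controlled trial of up to 130 sexually active adolescent males aged 14-21 years" (Strategy and Sample).
- The efficacy analysis keeps "all randomized patients who complete follow up and were sexually active in the past 4 weeks" (Statistical Analysis Plan).
- Eligible males are those "who have been sexually active with females in the past 3 months" (Strategy and Sample), a longer look-back than the 4-week outcome window.
- On baseline data, the intervention-arm description says: "Participants will complete a baseline questionnaire to assess demographics, access to care, as well as sexual behaviors, beliefs, and attitudes". It does not say whether 4-week encounter and condom counts are among the items.

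**The concern.** The baseline value of an outcome is usually among its best predictors, and here it is cut to two levels while age stays continuous. A participant who never used a condom and one who used it nine times in ten fall in the same category. The flag can therefore explain less of the follow-up variation than the baseline proportion would. What is at stake is power, in an analysed set that can only be as large as or smaller than the number enrolled, and in a study that hopes to "show potential efficacy to increase condom use" (Study Purpose and Rationale).

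**Working it through.** **Inputs.** The outcome, covariates, maximum of 130, analysis set and look-back windows come from the documents. The documents give no significance level, power, effect size, retention, encounter frequency or baseline-to-follow-up correlation. There is thus no planned figure to reproduce, and everything below is assumed and varied.

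**Step 1: what the flag discards.** With one encounter the proportion can only be 0 or 1, so flag and proportion are identical. With two it can be 0, 0.5 or 1, and the flag merges the first two. With ten it merges ten of the eleven possible values. In simulation, 18-28% of baseline proportions lay strictly between 0 and 1 at a mean of 2 encounters, and 44-66% at a mean of 5.

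**Step 2: from explained variance to power.** Take a flag model with 80% power at two-sided 5%. Adding the proportion multiplies residual variance by r = (1 - R²both) / (1 - R²flag), and power becomes Φ[(1.960 + 0.842)/√r - 1.960]. The R² values come from correlated beta-binomial data (mean use 0.4, concentration 1, everyone with a baseline proportion):

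| Latent correlation | Encounters | R² flag | R² flag + proportion | r | Power |
|---|---|---|---|---|---|
| 0.5 | 1 | 0.053 | 0.053 | 1.000 | 80.0% |
| 0.5 | 2 | 0.070 | 0.090 | 0.910/0.930 = 0.978 | 80.9% |
| 0.5 | 5 | 0.077 | 0.145 | 0.855/0.923 = 0.926 | 82.9% |
| 0.5 | 10 | 0.073 | 0.175 | 0.825/0.927 = 0.890 | 84.4% |
| 0.8 | 1 | 0.144 | 0.144 | 1.000 | 80.0% |
| 0.8 | 2 | 0.199 | 0.257 | 0.743/0.801 = 0.928 | 82.9% |
| 0.8 | 5 | 0.214 | 0.403 | 0.597/0.786 = 0.760 | 89.5% |
| 0.8 | 10 | 0.186 | 0.482 | 0.518/0.814 = 0.636 | 94.0% |

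The gain is nil at one encounter, small at two, and material only with more encounters and stable behaviour.

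**Step 3: the model itself.** This was simulated as a fractional logit with robust standard errors, tested at 5%. Assumed 75% followed up and 76% of those recently active: 0.75 × 0.76 = 0.57, and 0.57 × 130 ≈ 74 analysed. Control use was 47.5% and the arm difference 20 points. The spread of behaviour and its stability over time were varied. Change in power from adding the proportion beside the flag:
- 2 encounters per 4 weeks: about -1 to +3 points
- 5 encounters: about 0 to +13
- 8 encounters: about +2 to +18

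Monte Carlo error of such differences is 0.3-0.9 points, so the small losses are not distinguishable from zero.

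**Step 4: participants without a baseline proportion.** Someone eligible on the 3-month window but with no intercourse in the 4 weeks before baseline has a proportion of 0/0. If the proportion replaces the flag (with a missing indicator, and the flag known for all), the best case at 5 encounters falls from +13.4 points with none lacking to +7.4 with 20% lacking and +2.5 with 40%. Over 96 scenarios with 0, 20 or 40% lacking, replacement ranged from -3.3 to +18.9 points. Keeping the flag and adding the proportion, set to its mean where lacking, ranged from -1.0 to +18.6 (worst -1.3 in further sensitivity runs). Each option costs one extra parameter.

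**Step 5: validity and what is estimated.** With no true effect and 80 or 130 analysed, rejection rates were 4.7-5.6% with the flag and 4.7-5.7% with flag plus proportion. Their Monte Carlo error is √(0.05 × 0.95/1,500) ≈ 0.6 points. With an effect, 80 analysed and a mean of 8 encounters, power rose from 71.6% to 80.6% while the median log odds ratio moved from 0.908 to 1.028. When the proportion replaced the flag, the median standard error of the log odds ratio changed by only 0.000 to +0.015 at 2 encounters and -0.005 to +0.014 at 5. The power gain thus comes largely from a conditional odds ratio further from 1, with little help from a tighter interval.

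**The case against.** The strongest reply is that nothing here is an error. A binary baseline covariate, named in advance, is legitimate. The study is a pilot with no power target, and preferring one valid covariate to another is partly taste. That stands, and it is why the point is optional and of low priority.

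The reply can add that every quantity driving the gain is absent from the documents, so the calculations cannot show that this trial would benefit. That also stands. The results show when a gain would occur and that the downside is small.

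A further objection is that the change may not be cheap or even possible. The documents name only sexual behaviours as a baseline topic, and counts not asked for cannot be recovered for anyone already enrolled. This is correct, and the recommendation is conditional on it.

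Finally, an analyst reporting an odds ratio with its interval may see no narrower interval and a slightly different estimand. This is a genuine cost. It does not remove the gain in the test of arm effect where encounters are frequent and behaviour is stable.

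A reader might go the other way and infer that the coarse flag biases the arm comparison. The documents do not support that: allocation is randomised and concealed, and coarsening a baseline covariate leaves the comparison valid. Any bias from restricting the analysis to recently active completers is a separate question that neither covariate settles.

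**Conclusion.** The point holds as an inexpensive, optional improvement. The primary model discards information on baseline condom use, and nothing else in the plan restores it. Keeping the flag and adding the baseline proportion is expected to change power by roughly -1 to +3 points at 2 encounters per 4 weeks, 0 to +13 at 5 and +2 to +18 at 8. The upper ends require behaviour that is stable from baseline to follow-up. The gain is smaller when many lack a baseline proportion, and nil when participants report about one encounter.

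These figures rest on about 74 analysed, 47.5% control use, a 20-point difference, and assumed encounter frequency and correlation. None of these is in the documents. A reader might infer that the trial forgoes some 18 points of power, or that its interval would tighten. Neither follows: the first is the best case of an assumed range, and the log-odds-ratio interval does not generally narrow.

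**What to change.** First establish whether the baseline questionnaire records the number of encounters and of condom uses over 4 weeks. If it does not, leave the flag as it is.

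If it does, add to the Statistical Analysis Plan, before outcomes are seen:
- The primary model keeps the consistent-use flag and adds the baseline proportion (condom uses over encounters) as a continuous covariate. The proportion is set to its mean for participants with no intercourse in the 4 weeks before baseline.
- If the flag is also undefined for those participants, use the proportion plus a missing indicator instead. Choosing between the two requires stating the flag's recall window, which the plan leaves open.
- The consistent-use outcome keeps the flag alone.
- The covariate for condom use at last intercourse is named explicitly, since the plan applies the same model to it.

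The cost is a few lines of text and one extra parameter. The conditional odds ratio differs slightly from that of the flag-only model because odds ratios are non-collapsible, so the report should state which covariates it is conditional on.
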